Clinical Trial Protocol

Document Number:		c34982691-03
BI Trial No.	1425-0008	
BI Investigational Medicinal Product	BI 706321	
Title	Safety, tolerability, and pharmacokinetics of single rising oral dose and multiple rising oral doses of BI 706321 in healthy Japanese male subjects and single oral dose of BI 706321 in healthy Chinese male subjects (double-blind, randomised, placebo-controlled, parallel group design)	
Lay Title	A study in healthy Japanese and Chinese men to test how well different doses of BI 706321 are tolerated	
Clinical Phase	I	
Clinical Trial Leader	 Telephone: [REDACTED], Fax: [REDACTED]	
Investigator	 Phone: [REDACTED] Fax: [REDACTED]	
Status	Final Protocol / Revised Protocol (based on global amendment 2)	
Version and Date	Version: 3.0	Date: 10 December 2021
Page 1 of 87		

Proprietary confidential information © 2021 Boehringer Ingelheim International GmbH or one or more of its affiliated companies. All rights reserved. This document may not - in full or in part - be passed on, reproduced, published or otherwise used without prior written permission
		

CLINICAL TRIAL PROTOCOL SYNOPSIS

Company name	Boehringer Ingelheim
Protocol date	03 Aug 2021
Revision date	10 Dec 2021
BI trial number	1425-0008
Title of trial	Safety, tolerability, and pharmacokinetics of single rising oral dose and multiple rising oral doses of BI 706321 in healthy Japanese male subjects and single oral dose of BI 706321 in healthy Chinese male subjects (double-blind, randomised, placebo-controlled, parallel group design)
Investigator	[REDACTED] Phone: [REDACTED] Fax: [REDACTED]
Trial site	SOUSEIKAI Sumida Hospital
Clinical phase	I
Trial rationale	
Part I:
 
The trial is required to assess the safety, tolerability, and pharmacokinetics of BI 706321 administered in multiple rising oral doses to healthy Japanese male subjects in order to provide the basis for the clinical development of BI 706321 for the treatment of Crohn's disease in Japan.
 
Part II:
 
The trial is required to assess the safety, tolerability, and pharmacokinetics of BI 706321 administered in single oral dose to healthy Chinese male subjects in order to provide the basis for the clinical development of BI 706321 for the treatment of Crohn's disease in China.

Trial objectives	To investigate safety, tolerability and pharmacokinetics following single and multiple rising doses of BI 706321

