4.1.4 Drug assignment and administration of doses for each subject

Part I:

The treatments to be evaluated are outlined in Table 4.1.4: 1 below. The number of units for placebo corresponds to the number of units of the corresponding dose level.

Table 4.1.4: 1 BI 706321 and placebo treatments, oral administration

Dose group	Substance	Pharmaceutical form	Unit strength	Number of units per administration	Total dose
1	BI 706321	Film-coated tablet	2 mg	1 tablet	2 mg
2	BI 706321	Film-coated tablet	5 mg	1 tablet	5 mg
3	BI 706321	Film-coated tablet	1 mg 2 mg 5 mg	1 tablet each	8 mg
4	BI 706321	Film-coated tablet	5 mg	2 tablets	10 mg
1-4	Placebo*	Film-coated tablet	--	identical to active treatment	--

* Subjects receiving placebo are equally distributed across dose groups

Proprietary confidential information © 2021 Boehringer Ingelheim International GmbH or one or more of its affiliated companies

The trial will be divided into two parts (single dose and multiple dose). During the single dose part (Days 1 to 6), subjects will receive one single dose of BI 706321 (or placebo) on Day 1. The multiple dose part starts on Day 6 and subjects will receive a dose of 2 to 10 mg of BI 706321 (or placebo) once daily for 14 days (Days 6 to 19).

Administration of trial medication will be performed after subjects have fasted overnight; fasting is to start no later than 10 h before the scheduled dosing. The investigator (or authorised designee) will administer the trial medication as an oral dose together with about 240 mL of water to subjects who are in a standing/sitting position. During the first 4 h after drug administration for the single dose part, subjects are not allowed to lie down (i.e. no declination of the upper body of more than 45 degrees from upright posture except for medical examination) or to sleep. For drug administration, the so-called four-eye principle (two-person rule) should be applied. For this, 1 authorised employee of the trial site should witness the administration of trial medication, and – if applicable – its preparation (e.g. reconstitution), if correct dosage cannot be ensured otherwise. To ensure a dosing interval of 24 h, the administration of trial medication should take place at the same time every day.

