7.3.4 Safety analyses

Safety will be assessed as defined by the endpoints listed in Section [2.1.2](#) and [2.2.2](#) based on the treated set (TS). Safety analyses will be descriptive in nature and will be based on BI standards.

For all analyses the treatment actually administered (= treatment at onset) to the subject will be used (any deviations from the randomised treatment will be discussed in the minutes of the Report Planning Meeting).

Treatments will be compared in a descriptive way. The placebo group in the safety evaluation will consist of all subjects treated with placebo, regardless of the dose group in which they were treated. The test treatment groups will be compared to the placebo group in a descriptive way. Tabulations of frequencies/proportions will be used for the evaluation of categorical (qualitative) data, and tabulations of descriptive statistics will be used to analyse continuous (quantitative) data.

Measurements (such as ECGs, vital signs, or laboratory parameters) or AEs will be assigned to treatments (see Section [4.1](#)) based on the actual treatment at the planned time of the measurement or on the recorded time of AE onset (concept of treatment-emergent AEs). Therefore, measurements planned or AEs recorded prior to first intake of trial medication will be assigned to the screening period, those between the first trial medication intake and end of REP (see Section [1.2.2](#)) will be assigned to the treatment period. Events occurring after the REP but prior to trial termination date will be assigned to 'follow-up'. These assignments including the corresponding time intervals will be defined in detail in the TSAP. Note that AEs occurring after the last per protocol contact but entered before database lock will be reported to Pharmacovigilance only and will not be captured in the trial database.

Additionally, further treatment intervals (called analysing treatments) may be defined in the TSAP in order to provide summary statistics for other than above periods, such as combined treatments, on-treatment totals, or periods without treatment effects (such as screening and post-study intervals).

Proprietary confidential information © 2021 Boehringer Ingelheim International GmbH or one or more of its affiliated companies

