5.2.2 Secondary endpoints

Pharmacokinetic endpoints for BI 706321 are defined as secondary endpoints of the trial.

Section 2.1.3 of the CTP:

The following pharmacokinetic parameters will be determined if feasible:

Part I

Single dose part (after the first dose):

- $AUC_{0-\infty}$ (area under the concentration-time curve of the analyte in plasma over the time interval from 0 extrapolated to infinity)
- C_{max} (maximum measured concentration of the analyte in plasma)
- t_{max} (time from dosing to maximum measured concentration of the analyte in plasma)

After the last dose:

- $AUC_{\tau,ss}$ (area under the concentration-time curve of the analyte in plasma at steady state over a uniform dosing interval τ)
- $C_{max,ss}$ (maximum measured concentration of the analyte in plasma at steady state over a uniform dosing interval τ)
- $C_{min,ss}$ (minimum concentration of the analyte in plasma at steady state over a uniform dosing interval τ)
- $R_{A,Cmax}$ (accumulation ratio based on $C_{max,ss}$)
- $R_{A,AUC}$ (accumulation ratio based on $AUC_{0-\tau}$)

Safety and tolerability endpoints

[figure not shown]
Section 2.2.2.1 of the CTP:

Safety and tolerability of BI 706321 will be assessed based on:

- *AEs (including clinically relevant findings from the physical examination)*
- *Safety laboratory tests*
- *12-lead ECG*
- *Vital signs (blood pressure, pulse rate, body temperature)*

12-lead ECG endpoints:

For the definition of baseline and a summary of time points scheduled for ECG recording and central evaluation please refer to [Section 6.7](#).

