6. GENERAL ANALYSIS DEFINITIONS

6.1 TREATMENTS

For basic study information on treatments to be administered, assignment of treatment groups and selection of doses, please see CTP, Sections 3 and 4.

In Part I, a double-blind, randomised and placebo-controlled parallel-group trial in Japan is planned.

A total of 48 Japanese healthy male subjects will be treated with single and multiple doses of BI 706321. The subjects will be assigned to 4 dose groups of 12 subjects. In each dose group, 9 subjects will be randomised to active treatment and 3 subjects will be randomised to placebo. All subjects will receive a single dose on Day 1 (single dose evaluation), and further 2 weeks with daily doses of study treatment starting on Day 6 (multiple dose evaluation). For details of dosage and formulation see [Table 6.1: 1](#).

Table 6.1: 1 Treatments and labels used in the analysis – Part I

Treatment		Short label
P*	Placebo	Placebo – Japanese
A	BI 706321, 2 mg TABLET, FILM COATED QD ORAL	BI 2mg – Japanese
B	BI 706321, 5 mg TABLET, FILM COATED QD ORAL	BI 5mg – Japanese
C	BI 706321, 8 mg TABLET, FILM COATED QD ORAL	BI 8mg – Japanese
D	BI 706321, 10 mg TABLET, FILM COATED QD ORAL	BI 10mg – Japanese

* For data analysis purposes, the placebo control group of Part I (Japan) will include all subjects of all dose groups in Part I treated with placebo.

Section 1.2.2 of the CTP:

*The Residual Effect Period (REP) of BI 706321 is 16 days and is projected based on 5*terminal t_{1/2} from preliminary PK data of Trial 1425-0002. This is the period after the last dose with measurable drug levels and/or pharmacodynamic effects still likely to be present.*

The following study phases will be defined for the analysis of adverse events (AEs):

- **Screening** (ranging from 0:00 h on day of informed consent until first administration of study medication (BI/Placebo))
- **On treatment** (ranging from the first time of administration of BI or Placebo until 16 days (384 hours) after the last time of administration of BI/Placebo)
- **Follow-up (F/U)** (ranging from 16 days (384 hours) after last administration of BI or Placebo until 0:00 h on day after trial termination date)

In Part I, the end-of-trial visit is planned to take place on day 27, whereas last drug administration is planned on day 19. Consequently, follow-up phase does not apply to Part I.

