Section 7.3.4 of the CTP: *Note that AEs occurring after the last per protocol contact but entered before database lock will be reported to Pharmacovigilance only and will not be captured in the trial database.*

Displays of AEs will be stratified by treatment group as specified in [Table 6.1: 1](#). The results will be presented separately for each trial part if not stated otherwise. The following AE displays will be provided in the report:

In Section 15.3 and Appendix 16.1.13.1.8 (for ClinicalTrials.gov) of the CTR displays, the on treatment phase will be analysed (labelled with the name of the study treatment (short label)). Screening and follow-up phases will not be included in this analysis.

The following totals will be provided for Section 15.3 (except for ECG analysis):

- a total over all on treatment phases (“**Total**”)
- a total over all on treatment phases with BI (“**BI Total**”) (for Part I only)

In Section 15.4 and Appendix 16.2 (Listings) of the CTR displays, the screening and follow-up will additionally be included and no totals will be provided.

For detailed information on the handling of the treatments refer to Technical TSAP ADS (analysis data set) plan and Analysis Data Reviewers guide.

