7.8.1 Adverse Events

AEs will be coded using MedDRA. The coding version number will be displayed as a footnote in the respective output.

Unless otherwise specified, the analyses of AEs will be descriptive in nature. All analyses of AEs will be based on the number of subjects with AEs and NOT on the number of AEs. BI standards as presented in “Analysis and Presentation of Adverse Event Data from Clinical Trials – Display Template” [BI-KMED-BDS-HTG-0041] (9) and [BI-KMED-BDS-HTG-0066] (10) will be applied.

The analysis of AEs will be based on the concept of treatment emergent AEs. That means that all AEs will be assigned to ‘screening’, ‘on treatment’ and ‘follow-up’ phases as defined in [Section 6.1](#). AEs will be analysed based on actual treatments, as defined in [Table 6.1: 1](#).

According to the clinical study protocol, adverse events of special interest (AESI) will be analysed:

Section 5.2.5.1.4 of the CTP: *The following are considered as AESIs:*

- Hepatic injury
A hepatic injury is defined by the following alterations of hepatic laboratory parameters:
 - o *An elevation of AST (aspartate transaminase) and/or ALT (alanine transaminase) ≥ 3 -fold ULN combined with an elevation of total bilirubin ≥ 2 -fold ULN measured in the same blood sample, or*
 - o *Aminotransferase (ALT, and/or AST) elevations ≥ 10 fold ULN*

According to ICH E3 (11), in addition to Deaths and Serious Adverse Events, ‘other significant’ AEs need to be listed in the clinical trial report. These will be any non-serious adverse event that led to an action taken with study drug (e.g. discontinuation or dose reduced or interrupted).

An overall summary of AEs will be presented.

The frequency of subjects with AEs will be summarised by treatment, primary system organ class (SOC) and preferred term (PT). Separate tables will be provided for subjects with serious AEs, for subjects with drug-related AEs, for subjects with drug-related serious adverse events and for subjects with AESIs. In addition, the frequency of subjects with AEs will be summarised by treatment, worst intensity, primary system organ class (SOC) and preferred term (PT).

The system organ classes will be sorted alphabetically, PTs will be sorted by frequency (within SOC).

In addition, frequencies of subjects with non-serious AEs that had an incidence of $> 5\%$ for at least one treatment will be summarised by treatment, primary SOC and PT.

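### Should the adverse-event tables be split between the Day 1 single dose and the 14-day multiple-dose period?

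*SAP*

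**What the plan says.** The protocol title refers to "single rising oral dose and multiple rising oral doses of BI 706321 in healthy Japanese male subjects", and the synopsis gives the objective as "To investigate safety, tolerability and pharmacokinetics following single and multiple rising doses of BI 706321". Protocol 4.1.4 says of Part I: "The trial will be divided into two parts (single dose and multiple dose"), with one dose on Day 1 and daily dosing on Days 6 to 19. The SAP keeps that division for the pharmacokinetic endpoints, where 5.2.2 has a block headed "Single dose part (after the first dose") and another for the last dose.

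For AEs, SAP 6.1 defines screening, on treatment and follow-up. The on-treatment phase is a single interval, "ranging from the first time of administration of BI or Placebo until 16 days (384 hours) after the last time of administration". The same section says "Displays of AEs will be stratified by treatment group as specified in" Table 6.1: 1, which lists placebo and the four dose levels. SAP 7.8.1 adds: "The frequency of subjects with AEs will be summarised by treatment, primary system organ class (SOC) and preferred term (PT"), with further tables for serious, drug-related, drug-related serious and special-interest events and for worst intensity. None is split by dosing period.

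Three protocol sections settle the matter. Section 2.1.1 states the Part I main objective as safety, tolerability and pharmacokinetics after multiple rising doses over 14 days. Section 2.1.2 sets the primary endpoint as one percentage of subjects with drug-related AEs, with no reference to period. Section 7.3.4 counts everything from first intake to the end of the residual effect period as the treatment period, and then says that "further treatment intervals (called analysing treatments) may be defined in the TSAP in order to provide summary statistics for other than above periods".

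**The concern.** A reader who starts from the title and synopsis expects a safety result for the single dose and another for repeated dosing. The design has both stages and the pharmacokinetic endpoints follow them, but the AE tables do not. A pooled count of k subjects out of 9 fits any number from 0 to k with onset before the Day 6 dose. Part II, the stand-alone single-dose part, was cancelled (SAP 4), so Days 1 to 6 of Part I are the only single-dose experience this trial will provide.

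If the protocol had promised a separate single-dose AE incidence, its absence from the SAP would leave an objective unanswered. The effect of one dose could then not be told apart from that of accumulated exposure in any summary table.

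**Working it through.** **1. Does one on-treatment phase follow from the plan's own residual effect period?** Protocol 1.2.2 gives 16 days, based on 5 × terminal half-life in trial 1425-0002. The longest steady-state half-life in Table 1.2.1: 2 is 76.5 h, so 5 × 76.5 = 382.5 h, and 382.5 / 24 = 15.9 days. The stated 16 days (384 h) is reproduced.

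The gap from the Day 1 dose to the Day 6 dose is 120 h (5 days), shorter than 384 h. The single-dose half-lives in the same table (36.3 to 43.2 h) give the same answer: 5 × 36.3 = 181.5 h and 5 × 43.2 = 216 h, both above 120 h. Under the protocol's treatment-emergent rule, Day 6 falls while the Day 1 dose still counts as active. One continuous phase is what the rule implies.

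**2. How clean would a cut at Day 6 be?** From Table 1.2.1: 2, assuming mono-exponential decline from 24 h, the fraction of the single-dose 24 h concentration left at 120 h is 2^(−96 / half-life):

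- Single-dose half-lives of 40.8, 41.7, 36.3 and 43.2 h (2, 5, 8 and 10 mg): 20%, 20%, 16% and 21%.
- Steady-state half-lives of 74.4, 70.4, 46.8 and 76.5 h: 41%, 39%, 24% and 42%.

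Relative to the steady-state trough the residue looks smaller. At 2 mg with the single-dose half-life, 1.27 × 2^(−96/40.8) / 3.12 = 8.0%. Across doses the range is 3.7% to 8.0% with single-dose half-lives and 5.6% to 16.6% with steady-state half-lives. That denominator is reached only after accumulation, though, and Protocol 1.2.1 describes a multiphasic decline. A cut at Day 6 is workable but does not separate the two exposures cleanly.

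**3. Would the two percentages be comparable?** By the Part I flow chart, observation runs from 0 to 624 h. The single-dose stage is 120 / 624 = 19.2% of that time with 1 of 15 doses; the rest is 504 / 624 = 80.8% with 14 doses. The rates would refer to very different lengths of observation and would be imprecise. The exact 95% upper limit for 0/9 is 1 − 0.025^(1/9) = 33.6%, and for 0/36 it is 1 − 0.025^(1/36) = 9.7%.

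**4. How much does pooling hide in the precedent?** Trial 1425-0002 also gave a single dose, a five-day washout and 14 daily doses (Table 1.2.1: 4):

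- Any AE on active drug: 3 + 5 + 6 + 5 = 19 of 32 (59.4%).
- Drug-related AE on active drug, the primary endpoint here: 1 + 0 + 0 + 0 = 1 of 32 (3.1%).

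The single-dose share is therefore bounded by 0% and 59.4% for any AE, but by 0% and 3.1% for the primary endpoint.

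**5. Is safety in Days 1 to 6 otherwise visible?** Laboratory data, vital signs and ECG intervals are summarised by planned time point (SAP 7.8.2 to 7.8.4). QTcF is estimated at the single-dose peak and at the steady-state peak (SAP 7.8.4). AE onset times are recorded (Protocol 5.2.5.2.1), dosing times are listed (SAP 7.7), and individual listings are planned (SAP 7).

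**The case for a change.** The strongest contrary case is that AEs are the one safety domain without a summary over time, although SAP 6.1 itself labels Day 1 as the single-dose evaluation and Day 6 onward as the multiple-dose evaluation. Timing could matter. In trial 1425-0002 AUC accumulated 2.30- to 3.69-fold, CRP rises began after about 3 to 6 days of multiple dosing, and five active subjects but no placebo subject had flu-like symptoms. One period variable and one table would show this, and Protocol 7.3.4 allows it without an amendment.

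The 3.1% is also a precedent, not a forecast. Protocol 1.2.1 reports drug-related AEs in 1 + 1 + 1 + 2 = 5 of 46 active subjects (10.9%) in part I of the single-dose trial, and in 8 of 14 (57.1%) in the itraconazole interaction trial.

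What stands is that such a table would be informative and cheap. It does not follow that the plan is wrong without it. Naming both kinds of dosing in a title and synopsis does not commit the sponsor to separate AE incidences when the detailed objective, the endpoint and the analysis section specify one period. The cancellation of Part II adds nothing either: it was a Chinese cohort at 10 mg only, so no Japanese single-dose data were lost. In addition, SAP 4 had the Part I analysis finalised directly after Part I, so a table added now could be post hoc.

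**Conclusion.** The concern does not hold. It is true that no AE table in the visible SAP is split at Day 6, but the SAP carries out what Protocol 7.3.4 prescribes, and leaving an optional interval undefined is not an error. The pooled percentage is a valid incidence for the whole regimen of 15 doses and answers the primary endpoint as written. No sample size, error rate or estimate changes, since the trial tests no hypotheses. What remains is a preference for one more descriptive display, which can be built from data already collected.

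This rests on reading Protocol 2.1.1 as the governing statement of the Part I objective, and on the visible SAP. The sponsor's display templates and the technical data-set plan to which the SAP refers were not available, and nothing is inferred from their absence.

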6.2 IMPORTANT PROTOCOL DEVIATIONS

Data discrepancies and deviations from the CTP will be identified for all treated subjects. Consistency check listings (for identification of deviations of time windows) and a list of protocol deviations (e.g. deviations in drug administration, in blood sampling times, etc.) will be provided to be discussed at the Report Planning Meeting (RPM). At this meeting, all manual deviations identified at the sites by the CRAs and deviations too complex to program will be reviewed by the trial team to decide which are considered important. For definition of important protocol deviations (iPD), and for the process of identification of these, refer to the Boehringer Ingelheim (BI) SOP "Identify and Manage Important Protocol Deviations (iPD)" ([2](#)).

Section 7.3 of the CTP: *Important protocol deviation (iPD) categories will be specified in the DV domain, iPDs will be identified no later than in the Report Planning Meeting, and the iPD categories will be updated as needed.*

If any iPDs are identified, they are to be summarised into categories and will be captured in the iPD specification file (DV domain) and in the decision log. The iPD specification file will be stored within the TMF in EDMS.

The iPDs will be summarized and listed in the CTR.

6.3 SUBJECT SETS ANALYSED

Section 7.3 of the CTP:

- **Treated set (TS):** *The treated set includes all subjects who were randomized and treated with at least one dose of study drug. The treatment assignment will be determined based on the first treatment the subjects received. The treated set will be used for safety analyses.*
- **Pharmacokinetic parameter analysis set (PKS):** *This set includes all subjects in the treated set (TS) who provide at least one PK endpoint that was not excluded due to a protocol deviation relevant to the evaluation of PK or due to PK non-evaluability (as specified in the following subsection 'Pharmacokinetics'). Thus, a subject will be included in the PKS, even if he/she contributes only one PK parameter value for one period to the statistical assessment. Descriptive and model based analyses of PK parameters will be based on the PKS.*

All ECG analyses are performed on the TS, except for the exposure-response analyses, which will be performed on the ECG Pharmacokinetic Concentration Set (ECGPCS) defined below.

- **ECG PK concentration set (ECGPCS):** *This subject set includes all subjects from the TS who provide at least one pair of a valid drug plasma concentration and a corresponding (i.e. time-matched) ECG endpoint to be used in the exposure-response analyses. For placebo subjects, the plasma concentration is set to zero and hence always considered as valid. The decision whether a time deviation between PK blood sampling and ECG recording is acceptable (and thus whether the pair of values will be used) is to be made no later than at the RPM before database lock. The ECGPCS will be used for the exposure-response analyses.*

Section 7.3 of the CTP:

The pharmacokinetic parameters listed in CTP Section 2.1.3 and 2.2 for drug BI 706321 and BI 706062 will be calculated according to BI Standards.

Plasma and urine concentration data and parameters of a subject will be included in the statistical pharmacokinetic (PK) analyses if they are not flagged for exclusion due to a protocol deviation relevant to the evaluation of PK (to be decided no later than in the Report Planning Meeting) or due to PK non-evaluability (as revealed during data analysis, based on the criteria specified below). Exclusion of a subject's data will be documented in the CTR.

Relevant protocol deviations may be

- *Incorrect trial medication taken, i.e. the subject received at least one dose of trial medication the subject was not assigned to*
- *Incorrect dose of trial medication taken*
- *Use of restricted medications*

[figure not shown]
Plasma and urine concentrations and/or parameters of a subject will be considered as non-evaluable, if for example

- *The subject experienced emesis that occurred at or before two times median t_{max} of the respective treatment (Median t_{max} is to be determined excluding the subjects experiencing emesis),*
- *Missing samples/concentration data at important phases of PK disposition curve.*

Plasma/urine concentration data and parameters of a subject which is flagged for exclusion will be reported with its individual values but will not be included in the statistical analyses.

Table 6.3: 1 Subject sets analysed

Class of endpoint	Analysis sets		
	TS	PKS	ECGPCS
Primary endpoint and further safety assessments (incl. central ECG)	X		
Analyses of PK endpoints		X	
ECG exposure response analysis			X
Disposition	X		
Demographic/baseline parameters	X		
Important protocol deviations	X		
Exposure	X		

